9.1.3. The Clinical Global Impressions-Severity

The CGI-S ([Guy 1976](#)) is a clinician-rated scale used to rate the severity of the patient’s current state of mental illness compared with a patient population with MDD ([Appendix 9](#)). The participant will be rated on a scale from 1 to 7 with 1 indicating a “normal, not at all ill” and 7 indicating “among the most extremely ill patients.” The CGI-S will be administered by the investigator or a sub-investigator with extensive professional training and experience in assessing mental illness and qualification standards set by the sponsor and rater training vendor. For Part A and Part B, at Screening (Visit 1) and Visit 2, the CGI-S will be administered with a look-back timeframe of 1 week. At all other evaluations, the CGI-S will be administered with a look-back timeframe of “since last evaluation.”

CGI-S assessments will be performed as specified in the schedule of activities in Section [2.1](#) (Part A) and Section [2.2](#) (Part B).

9.1.4. The Hamilton Anxiety Rating Scale (Part A Only)

The HAM-A ([Hamilton 1959](#)) is a clinician-rated scale to rate the severity of anxiety symptoms ([Appendix 14](#)). The participant will be tested using 14 questions, and responses will be rated on a

scale from 0 to 4, with 0 indicating “none” (ie, no anxiety) and 4 indicating a response of “severe, gross disabling” anxiety. The HAM-A will be administered at Visit 2, Visit 3, Visit 4, and Visit 6 by the investigator or a sub-investigator with extensive professional training and experience in assessing mental illness and qualification standards set by the sponsor and rater training vendor. The HAM-A will be collected only from participants entering the study after the amendment has been IRB approved.

9.1.5. Likert Patient Depressive Symptom Scales (Part B Only)

The Likert Patient Depressive Symptom Scales are a set of questions framed in a Likert format, which is the most widely used approach to scaling responses in survey research aimed to capture the full domain/indication under study. In the BID cohort part of the study, a set of Likert Patient Depressive Symptom Scales will be used to collect the participant self-reported outcomes on domains related to MDD, including depression, anxiety, and sleep quality ([Appendix 15](#)). The Likert Patient Depressive Symptom Scales will be completed by the research participant as specified in the schedule of activities in Section [2.2](#).

During the outpatient double-blind treatment week and the safety follow-up, the Likert Patient Depressive Symptom Scale questions will be provided to the participants in a diary to be completed at home.

9.1.6. Hopkins Verbal Learning Test-Revised (Part B Only)

The HVLT-R is the most recent ([Shapiro et al 1999](#)) version of the verbal learning and episodic memory test. It includes 6 different forms aimed to reduce practice effects, which this trial will employ in respective study visits. The HVLT-R is comprised of immediate recall trials of 12 nouns with 3 different categories and a delayed recall followed by a recognition task ([Appendix 16](#)). For the immediate recall, on each trial, the participant is asked to say as many words enunciated by the rater administering the test as possible. For the delayed recall, after approximately 20 to 25 minutes of the immediate recall trials, the participant is requested to evoke all words he/she can remember without any cues. The recognition trial is composed of 24 words, including 12 target words and 12 false-positives, and the participant is asked which of the 24 words were the ones read during the immediate recall trial. The HVLT-R will be administered by the trained site professional as specified in the schedule of activities in Section [2.2](#).

9.2. Adverse Events

The definitions of an AE or SAE can be found in [Appendix 4](#).

AEs will be reported by the participant (or, when appropriate, by a caregiver, surrogate, or the participant’s legally authorized representative).

The investigator and any designees are responsible for detecting, documenting, and recording events that meet the definition of an AE or SAE. Any AEs that are ongoing at the time of the final protocol-defined study visit will be followed until the condition returns to prestudy status, has resolved or stabilized, or can be explained as being unrelated to study treatment. If a

follow-up visit is deemed necessary for appropriate safety surveillance, it will take place within 30 days of the final protocol-defined study visit.

9.2.1. Time Period and Frequency for Collecting AE and SAE Information

All SAEs from the signing of the ICF will be collected at the timepoints specified in the schedule of activities (Section 2.1 [Part A] and Section 2.2 [Part B]), and as observed or reported spontaneously by study participants, until 30 days from the last dose of study treatment.

All AEs from the signing of the ICF will be collected at the timepoints specified in the schedule of activities (Section 2.1 [Part A] and Section 2.2 [Part B]), and as observed or reported spontaneously by study participants, until 30 days from the last dose of study treatment.

Medical occurrences that begin before the start of study treatment but after obtaining informed consent will be recorded on the AE section of the eCRF.

All SAEs will be recorded and reported to the sponsor or designee within 24 hours, as indicated in [Appendix 4](#). The investigator will submit any updated SAE data to the sponsor within 24 hours of it being available.

Investigators are not obligated to actively seek AE or SAE information in former study participants. However, if the investigator learns of any SAE, including a death, at any time after a participant has been discharged from the study, and he/she considers the event to be reasonably related to the study treatment or study participation, the investigator must promptly notify the sponsor.

The method of recording, evaluating, and assessing causality of AEs and SAEs and the procedures for completing and transmitting SAE reports are provided in [Appendix 4](#).

9.2.2. Method of Detecting AEs and SAEs

Care will be taken not to introduce bias when detecting AEs and/or SAEs. Open-ended and non-leading verbal questioning of the participant is the preferred method to inquire about AE occurrences.

9.2.3. Follow-up of AEs and SAEs

After the initial AE/SAE report, the investigator is required to proactively follow each participant at subsequent visits/contacts. All AEs/SAEs will be followed until resolution, stabilization, until the event is otherwise explained, or the participant is lost to follow-up (as defined in Section 8.3).

The investigator is obligated to perform or arrange for the conduct of supplemental measurements and/or evaluations as medically indicated or as requested by the sponsor to elucidate the nature and/or causality of the AE or SAE as fully as possible. This may include additional laboratory tests or investigations, histopathological examinations, or consultation with other health care professionals.

If a participant dies during participation in the study or during a recognized follow-up period, the investigator will make every effort to provide the sponsor with a copy of any postmortem findings including histopathology.

New or updated information will be recorded in the originally completed eCRF.

The investigator will submit any updated SAE data to the sponsor within 24 hours of receipt of the information.

9.2.4. Regulatory Reporting Requirements for SAEs

- Prompt notification by the investigator to the sponsor of an SAE is essential so that legal obligations and ethical responsibilities towards the safety of participants and the safety of a study treatment under clinical investigation are met.
- The sponsor has a legal responsibility to notify both the local regulatory authority and other regulatory agencies about the safety of a study treatment under clinical investigation. The sponsor will comply with country-specific regulatory requirements relating to safety reporting to the regulatory authority, institutional review boards (IRBs)/independent ethics committees (IECs), and investigators.
- An investigator who receives an investigator safety report describing a SAE or other specific safety information (eg, summary or listing of SAEs) from the sponsor will review and then file it along with the investigator's brochure and will notify the IRB/IEC, if appropriate according to local requirements.

9.2.5. Pregnancy

- Site personnel must report every pregnancy in female participants, and female partners of male participants, from the time the participant signs the ICF until 30 days after the last dose of study treatment.
- Within 24 hours of learning of the pregnancy, the investigator must report the event to the sponsor on the Clinical Trial Pregnancy Form and fax or e-mail it to the SAE reporting fax number or e-mail provided on the title page of this protocol, even if no AE has occurred. The investigator should follow the procedures outlined in [Appendix 5](#).
- Abnormal pregnancy outcomes (eg, spontaneous abortion, fetal death, stillbirth, congenital anomalies, ectopic pregnancy) are considered SAEs.

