6.1. Inclusion Criteria

Participants are eligible to be included in the study only if all of the following criteria apply. Inclusion criteria apply to Parts A and B unless otherwise noted.

1. Written informed consent from the participant has been obtained prior to any study-related procedures (as described in [Appendix 3](#)).
2. Male or female participants must be 18 to 65 years of age, inclusive, at the time of signing the informed consent.
3. Meet DSM-5 criteria ([American Psychiatric Association 2013](#)) for MDD (based on confirmation from the modified SCID), with a current major depressive episode of at least 8 weeks and not exceeding 18 months in duration at Visit 1.
4. Have a minimum score of 26 on the rater-administered MADRS at both Screening (Visit 1) and Visit 2 (Day 1 in Part A and Day –1 [Baseline] in Part B).
5. Have a CGI-S score ≥ 4 at both Screening (Visit 1) and Visit 2 (Day 1 in Part A and Day –1 [Baseline] in Part B).
6. Part A: Have a negative serum β -human chorionic gonadotropin (β -hCG) pregnancy test at Screening (Visit 1) if a WOCBP. Part B: If a WOCBP, have a negative serum β -hCG pregnancy test at Screening (Visit 1) AND a negative urine pregnancy test on Day –1 (baseline), if more than a week has passed since the serum pregnancy test at Screening. If urine pregnancy test is positive on Day –1, then a serum β -hCG pregnancy test should be done for confirmation.
7. Female participants willing to minimize the risk of becoming pregnant for the duration of the clinical study and follow-up period. A female participant is eligible to participate if she is not pregnant, not breastfeeding, and at least one of the following conditions applies:
 - a. Not a WOCBP

OR

 - b. A WOCBP who agrees to follow the contraceptive guidance in [Appendix 5](#) during the treatment period and for at least 4 to 5 weeks after the last dose of study treatment.

8. Male participants willing to minimize the risk of inducing pregnancy for the duration of the clinical study and follow-up period. A male participant must agree to use contraception as detailed in [Appendix 5](#) of this protocol during the treatment period and for at least 10 weeks after the last dose of study treatment and refrain from donating sperm during this period.
9. Able, as assessed by the investigator, and willing to follow study instructions and likely to complete all required study visits.

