12.5. Appendix 5: Contraceptive Guidance and Collection of Pregnancy Information

Definitions

Woman of Childbearing Potential (WOCBP)

A woman is considered fertile following menarche and until becoming postmenopausal unless permanently sterile (see below).

Women in the following categories are not considered WOCBP

1. Premenarchal
2. Premenopausal female with 1 of the following:
 - Documented hysterectomy
 - Documented bilateral salpingectomy
 - Documented bilateral oophorectomy
3. Postmenopausal female
 - A postmenopausal state is defined as no menses for 12 months without an alternative medical cause. A high FSH level in the postmenopausal range may be used to confirm a postmenopausal state in women not using hormonal contraception or HRT. However, in the absence of 12 months of amenorrhea, a single FSH measurement is insufficient.
 - Females on HRT and whose menopausal status is in doubt will be required to use one of the acceptable non-hormonal contraception methods if they wish to continue their HRT during the study. Otherwise, they must discontinue HRT to allow confirmation of postmenopausal status before study enrollment.

Contraception Guidance

Male Participants

- Male participants with female partners of childbearing potential are eligible to participate if they agree to ONE of the following during the study:
 - Are abstinent from penile-vaginal intercourse as their usual and preferred lifestyle (abstinent on a long term and persistent basis) and agree to remain abstinent
 - Vasectomy
 - Female partners of male study participants reliably use one of the following:
 - Hormonal contraceptives (ie, oral, patch, injection, implant)
 - Vaginal contraceptive ring

- Intrauterine device
- Bilateral tubal ligation
- Ensure placement with correct placement verified by hysterosalpingogram
- Surgical sterilization
- Male or female condom with spermicide
- Cap, diaphragm, or sponge with spermicide
- Men with a pregnant or breastfeeding partner must agree to remain abstinent from penile vaginal intercourse or use a male condom during each episode of vaginal intercourse during the study.
- Refrain from donating sperm for the duration of the study and for 10 weeks following the end of study.
- Refrain from attempting pregnancy with female for 10 weeks following the end of study.

Female Participants

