Female participants of childbearing potential are eligible to participate if they agree to use an acceptable method of contraception consistently and correctly, as listed below.

- Hormonal contraceptives (ie, oral, patch, injection, implant)
- Vaginal contraceptive ring
- Intrauterine device
- Bilateral tubal ligation
- Ensure placement with correct placement verified by hysterosalpingogram
- Surgical sterilization
- Male or female condom with spermicide
- Cap, diaphragm, or sponge with spermicide
- Abstinence (as described above)
- Male partner has vasectomy

Refrain from attempting pregnancy for 4 – 5 weeks following the end of study.

Pregnancy Testing

- WOCBP should only be included after a confirmed menstrual period and a negative highly sensitive serum pregnancy test.

- Additional pregnancy testing during the treatment period can be performed any time at the Investigator's discretion and after the last dose of study treatment.

Pregnancy testing will be performed whenever a menstrual cycle is missed or when pregnancy is otherwise suspected.

Collection of Pregnancy Information

Male Participants with Partners Who Become Pregnant

- The investigator will attempt to collect pregnancy information on any male participant's female partner who becomes pregnant while the male participant is in this study. This applies only to male participants who receive study treatment.
- After obtaining the necessary signed informed consent from the pregnant female partner directly, the investigator will record pregnancy information on the appropriate form and submit it to the sponsor within 24 hours of learning of the partner's pregnancy. The female partner will also be followed to determine the outcome of the pregnancy. Information on the status of the mother and child will be forwarded to the sponsor. Generally, the follow-up will be no longer than 6 to 8 weeks following the estimated delivery date. Any termination of the pregnancy will be reported regardless of fetal status (presence or absence of anomalies) or indication for the procedure.

Female Participants Who Become Pregnant

- The investigator will collect pregnancy information on any female participant who becomes pregnant while participating in this study. Information will be recorded on the appropriate form and submitted to the sponsor within 24 hours of learning of a participant's pregnancy.

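### The duty to report partner pregnancies ends 30 days after the last dose, 40 days short of the protocol's own 10-week male precaution period, and the related passages run on different clocks

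*Protocol*

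**What the plan says.** Four parts of the protocol bear on this.

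- **Reporting duty (Section 9.2.5).** Sites must report pregnancies in women in the trial and in "female partners of male participants, from the time the participant signs the ICF until 30 days after the last dose of study treatment". For procedures the section refers to Appendix 5.
- **Precautions in the eligibility criteria (Section 6.1).** Criterion 8 requires men to use contraception "for at least 10 weeks after the last dose of study treatment and refrain from donating sperm during this period". Criterion 7b requires women of childbearing potential to follow the contraceptive guidance "for at least 4 to 5 weeks after the last dose of study treatment".
- **Precautions in Appendix 5 (Section 12.5).** Men are told: "Refrain from attempting pregnancy with female for 10 weeks following the end of study". Women are told: "Refrain from attempting pregnancy for 4 – 5 weeks following the end of study". Both periods start at the end of study, not at the last dose.
- **Collection of pregnancy information in Appendix 5.** For men it covers any "female partner who becomes pregnant while the male participant is in this study". For women it says: "The investigator will collect pregnancy information on any female participant who becomes pregnant while participating in this study".

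Appendix 5 also states that a pregnancy is not in itself an adverse event or serious adverse event. Section 5.3 defines the end of the study for the trial as a whole: each part ends when its last participant terminates.

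**The concern.** A precaution period and a pregnancy-reporting period usually serve the same purpose. The first tries to prevent conception after dosing, and the second records the cases where prevention failed. Here the second stops well before the first for men. A partner pregnancy in the seventh week after the last dose would fall while the participant is still required to use contraception, yet no passage requires the site to tell the sponsor or follow the pregnancy to outcome.

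The trial is Phase 1b/2a, so few human pregnancy data can be expected and each case is informative. If uncomplicated pregnancies are not recorded, any abnormal outcome that does reach the sponsor has no denominator.

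The differing start points add a practical difficulty. A site asking how long to instruct a participant, and how long to report, gets different answers from Section 6.1, Section 9.2.5 and Appendix 5.

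**Working it through.** The plan gives no figure to reproduce. The check is day arithmetic on the stated periods.

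**Inputs**
- Reporting period: 30 days after the last dose (Section 9.2.5).
- Male precautions: at least 10 weeks = 70 days (criterion 8; Appendix 5).
- Female precautions: at least 4 to 5 weeks = 28 to 35 days (criterion 7b); 4 to 5 weeks in Appendix 5.
- Last scheduled visit: Day 22 with last dose on Day 15 (Part A), or Day 21 with last dose on Day 14 (Part B). Both give 7 days after the last dose.

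**Formula:** gap = precaution period − 30, both in days after the last dose.

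**Counted from the last dose (Section 6.1)**
- Men: 70 − 30 = 40 days; 40/70 = 57% of the period.
- Women, 4 weeks: 28 − 30 = −2 days, so reporting outlasts the precaution.
- Women, 5 weeks: 35 − 30 = 5 days; 5/35 = 14%.

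**Counted from the end of study (Appendix 5), taking that to mean the participant's final scheduled visit**
- Men: 70 + 7 = 77; 77 − 30 = 47 days; 47/77 = 61%.
- Women, 4 weeks: 28 + 7 = 35; 35 − 30 = 5 days; 5/35 = 14%.
- Women, 5 weeks: 35 + 7 = 42; 42 − 30 = 12 days; 12/42 = 29%.

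If end of study is read as Section 5.3 defines it, the Appendix 5 period has no fixed length for an individual, because it starts when the last participant in that part finishes.

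**Scope of collection in Appendix 5.** If being in the study ends at the final scheduled visit, collection stops 7 days after the last dose. That is 30 − 7 = 23 days before the Section 9.2.5 duty ends.

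**Does another passage close the gap?**
- Section 9.2.1 stops routine adverse event and serious adverse event collection at 30 days as well, and Appendix 5 keeps pregnancy itself out of both categories.
- Section 9.2.5 classes abnormal pregnancy outcomes as serious adverse events. After discharge, Section 9.2.1 requires a report if the investigator learns of a serious event and considers it reasonably related. Appendix 5 says the same for poststudy pregnancy-related serious events. Neither requires active inquiry.
- That leaves uncomplicated pregnancies, and abnormal outcomes judged unrelated, with no required route to the sponsor after 30 days. Follow-up to 6 to 8 weeks past the estimated delivery date is not triggered for them.

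**The case against.** The strongest reply is that contraception is an instruction to participants and Section 9.2.5 is a data-collection rule, so a site can comply with both. The 30 days match the adverse event collection period (Section 9.2.1) and the treatment-emergent cut-off (Section 10.3.5.1). The drug is described as rapidly cleared, with a short half-life (Introduction; Section 9.3). The protocol gives no rationale for 10 weeks. All of this stands. It means that the gap between Section 9.2.5 and criterion 8 is a mismatch of purpose, not an impossibility. A reader might infer that the protocol itself regards weeks 5 to 10 as a period of fetal exposure, but no passage says so.

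It can also be said that an early reproductive-safety signal would not simply vanish. That is correct. A reader might infer such a loss from the gap, but abnormal outcomes that the investigator learns of and judges related remain reportable without a time limit, although how this applies to partners is not spelled out.

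The practical yield is small. The last scheduled visit is 7 days after dosing, reports after that are spontaneous, and about 220 participants are planned (100 in Part A, 120 in Part B). This lowers the priority but does not remove the gap.

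Finally, the in-study wording in Appendix 5 may be loose drafting that was never meant to override the explicit 30 days. That is plausible, and it is a reason to correct the wording.

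**Conclusion.** The point holds for male participants. From the last dose, 40 of the 70 days of required precautions (57%) carry no duty to report a partner pregnancy. The figure is 47 of 77 days (61%) if Appendix 5's start point is taken as the final scheduled visit. Because criterion 8 sets a minimum of 10 weeks, these are lower figures.

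It should not be read as an equal problem for women. Measured from the last dose, their gap is nil at 4 weeks and 5 days at 5 weeks, reaching 5 to 12 days only on the Appendix 5 anchor.

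Separately, the passages disagree on the start of the precaution period (last dose or end of study) and on the scope of collection (30 days or while in the study). These inconsistencies do not depend on any view of how long exposure lasts.

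The results assume that final visits fall on their nominal days. Not captured means no duty to report; voluntary reports remain possible. No efficacy or safety analysis in the SAP is affected. Priority: minor.

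**What to change.** Reconcile Section 9.2.5, inclusion criteria 7 and 8 and Appendix 5:

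- Use one participant-level anchor throughout. If end of study is kept in Appendix 5, define it for the individual participant, because Section 5.3 defines it for the trial.
- Set the pregnancy-reporting period, chiefly for partner pregnancies, so that it does not end before the precaution period that the protocol itself sets.
- Carry the same period into Appendix 5's text on collecting pregnancy information, for partners and for female participants.

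Which length is right is for the sponsor to decide, and no view is taken here. The cost is amendment wording, a longer nominal reporting period, and follow-up of the few additional pregnancies that might be reported. No new visit or test is needed.
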